- t. Female patients of childbearing potential must have a negative serum pregnancy test at the Screening Visit and negative (urine or serum) pregnancy test within 72 hours prior to study Day 1. If the urine test is positive or cannot be confirmed negative, a serum pregnancy test will be required and must be negative for the patient to be eligible.
- u. Imaging performed prior to signing consent can be used for screening purposes if done within 8 weeks from signing consent. Baseline disease assessment using CT imaging (including brain assessment) is to be performed within 21 days of baseline.
- v. CT scan is not required at EOS if available within 4 weeks prior to the EOS Visit.
- w. If warranted for additional safety assessments, additional samples can be collected by the Investigator after discussion with the Sponsor. For patients who discontinue for reasons other than progressive disease, PK/ADA samples will be collected during post-treatment follow-up disease status until disease progression.
- x. To be collected pre-dose and then 2 (± 30 minutes) and 4 hours (± 1 hour) post end of infusion of ANV419.
- y. PK samples to be drawn pre-dose and then 15 minutes (±5 minute), 1 hour (±30 minutes), 2 hours (±30 minutes), 4 hours (±1 hour), and 8 hours (±1 hour) post end of infusion.

- z. PK samples to be drawn 24 hours (± 1 hour) post end of infusion.
- aa. PK samples to be drawn 72 hours (±1 hour) post end of infusion.
- bb. PK samples to be drawn pre-dose and then 1 hour (±30 minutes), and 2 hours (±30 minutes) post end of infusion.
- cc. Samples to be drawn pre-dose.
- dd.
- ee. All ADA samples to be taken pre-dose. Additional samples will be taken in the case of an IRR or irAE to rule out involvement of ADA.
- ff. If warranted for an additional PD assessment or if a PD visit is missed, an additional blood sample can be collected by the Investigator at a later visit after discussion with the Sponsor.
- gg. To be drawn
- hh. Tumor biopsies for research purpose may be performed within ± 3 days of the imaging assessment and within 7 days of the start of the dosing cycle if deemed safe and clinically feasible. Any tissue that is suspected to contain tumor, including lymph nodes, may be biopsied. All biopsies are optional.
- ii. Acetaminophen 1 g may be given to the patients as pre-medication or following the ANV419 infusion and can be used every 8 hours as needed.
- jj. A treatment interval of at least 12 days is required.

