#### *3.5.2 Pharmacokinetics Evaluation*

The following PK parameters will be estimated by non-compartmental approach using actual elapsed time from dosing for Cycle 1 only.

Following the interim analysis of the first part of the study (Part 1) using a data cut-off of October 17th, 2023, Anaveon has decided to not pursue the development of ANV419 in unresectable or metastatic melanoma. As a result, no pharmacokinetic data were generated after October 17th, 2023.

- $AUC_{0-\text{last}}$ : Area under the concentration-time curve ( $\mu\text{g}/\text{L} * \text{hours}$ ) from time zero (pre-dose) to the last measurable concentration, calculated using the trapezoidal method (as defined in Phoenix WinNonLin manual, Certara)
- $AUC_{0-\infty}$ : Area under the concentration curve ( $\mu\text{g}/\text{L} * \text{hours}$ ) from time zero (pre-dose) to infinity, calculated trapezoidal methods with linear interpolation (as defined in Phoenix WinNonLin manual, Certara) and extrapolated to infinity by addition of the last

quantifiable concentration divided by the elimination rate constant:  $AUC_{0-\text{last}} + C_{\text{last}}/\lambda_z$ . All the data measured will be reported and summarized;

- $\%AUC_{\text{ex}}$ : Percent of the area extrapolated for the calculation of  $AUC_{0-\infty}$ ;
- $C_{\text{max}}$ : Maximum concentration (ng/mL), obtained directly from the observed concentration versus time data;
- $T_{\text{max}}$ : Time to maximum concentration (hours), obtained directly from the observed concentration versus time data;
- $C_{\text{last}}$ : Last measurable concentration (ng/mL), obtained directly from the observed concentration versus time data;
- $T_{\text{last}}$ : Time (hours) of last concentration, obtained directly from the observed concentration versus time data;
- $t_{1/2}$ : half-life (hours), determined as  $\ln(2)/\lambda_z$ ;
- $V_{\text{ss}}$ : volume of distribution at steady state (L), calculated as Dose/ $(AUC_{0-\infty}\lambda_z)$ ;
- $\lambda_z$ : terminal elimination rate constant (1/hours), determined by linear regression of terminal points of the log-linear concentration-time curve. A minimum of three data points are required for determination of  $\lambda_z$ , with an r-square value  $\geq 0.7$ . In addition, visual assessment will be used to identify the terminal linear phase of the concentration-time profile.

For calculations using the trapezoidal rule, the following formula will be used:

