$$AUC = \frac{(C_1 - C_2)}{2}(t_2 - t_1)$$

For interpolation the following rule will be used if applicable

$$C^* = C_1 + \left| \frac{t^* - t_1}{t_2 - t_1} \right| (C_2 - C_1)$$

Where  $C^*$  is the concentration at time  $t^*$

Pharmacokinetic data will be reported by Think Q2. Details are included below but these outputs will not be created by Medpace.

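### The trapezoidal formula printed in SAP 3.5.2 subtracts the two concentrations where it should add them, and so contradicts the trapezoidal method that the same section cites

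*SAP*

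**What the plan says.** SAP 3.5.2 (Pharmacokinetics Evaluation) describes the AUC calculation in two ways.

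- **By reference to software.** AUC0-last is "calculated using the trapezoidal method (as defined in Phoenix WinNonLin manual, Certara"), and AUC0-∞ is "calculated trapezoidal methods with linear interpolation (as defined in Phoenix WinNonLin manual, Certara").
- **By a printed equation.** After the parameter list the SAP states: "For calculations using the trapezoidal rule, the following formula will be used". The equation is "AUC = \frac{(C_1 - C_2)}{2}(t_2 - t_1"), with a minus sign between the two concentrations.

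Other definitions in the section determine how far an error would spread:

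- AUC0-∞ is AUC0-last plus the last "quantifiable concentration divided by the elimination rate constant".
- %AUCex is the extrapolated share of AUC0-∞.
- The volume term is "volume of distribution at steady state (L), calculated as Dose" over the product of AUC0-∞ and λz.
- λz is "determined by linear regression of terminal points of the log-linear concentration-time curve", so it does not use the area.

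The interpolation rule printed just below the AUC equation is correct.

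**The concern.** The area under a straight line between two concentrations is their mean times the interval, (C1 + C2)/2 × (t2 − t1). The printed equation instead takes half the drop in concentration times the interval. It measures how fast the curve falls, not how much drug is present.

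AUC is one of the four PK parameters named in Protocol 8.2.7. SAP 3.5 assigns the PK work to external vendors, so this section is the written specification against which their output would be checked. SAP section 5 drops the Part 2 and Part 3 analyses and the iRECIST analysis, but not the Part 1 pharmacokinetics, so the section still applies.

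**Working it through.** **Step 1. The sign, with no assumptions.**

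| C1 | C2 | (C1 + C2)/2 × Δt | (C1 − C2)/2 × Δt |
|---|---|---|---|
| 100 | 100 | 100 Δt | 0 |
| 100 | 50 | 75 Δt | 25 Δt |
| 50 | 100 | 75 Δt | −25 Δt |
| 0 | 100 | 50 Δt | −50 Δt |

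The difference between the two rules is (C1 + C2)/2 × Δt − (C1 − C2)/2 × Δt = C2 × Δt. The printed rule therefore loses the later concentration times the interval on every segment. It can never overstate the area.

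**Step 2. Which parameters are affected.** AUC0-last is affected directly, and AUC0-∞, %AUCex and Dose/(AUC0-∞ × λz) through it. Cmax, Tmax, Clast and Tlast are read from the data, and λz and t1/2 come from the log-linear regression, so these six are unaffected.

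**Step 3. An illustration of size.** The documents state no AUC and no half-life, so there is no figure of the plan's own to reproduce. Inputs:

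- *Sampling:* pre-dose, then 0.25, 1, 2, 4, 8, 24 and 72 h after the end of infusion, from the Table 20 footnotes in Protocol Appendix A (for example "PK samples to be drawn 72 hours (±1 hour) post end of infusion"). The visits these footnotes attach to are not visible.
- *Infusion:* 15 minutes. This is stated for the combination part (SAP Table 2-4 note) and assumed here for Part 1.
- *Pre-dose value:* 0, in line with the SAP 3.5.4 rule for values below quantification before the first measurable one.
- *Model (assumed):* one compartment, half-life 2 to 168 h, k = ln 2/half-life, scaled so that a bolus of the same dose would start at 1. After the infusion, C(t) = [(1 − e^(−0.25k))/(0.25k)] × e^(−k(t − 0.25)), with t in hours from the start of infusion.

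Segments at a half-life of 24 h (k = 0.0289):

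| Interval (h from start) | C1 | C2 | Plus sign | Minus sign |
|---|---|---|---|---|
| 0–0.5 | 0 | 0.989 | 0.247 | −0.247 |
| 0.5–1.25 | 0.989 | 0.968 | 0.734 | 0.008 |
| 1.25–2.25 | 0.968 | 0.940 | 0.954 | 0.014 |
| 2.25–4.25 | 0.940 | 0.888 | 1.828 | 0.053 |
| 4.25–8.25 | 0.888 | 0.791 | 3.357 | 0.194 |
| 8.25–24.25 | 0.791 | 0.498 | 10.312 | 2.341 |
| 24.25–72.25 | 0.498 | 0.125 | 14.946 | 8.968 |
| AUC0-last (unrounded sum) | | | 32.38 | 11.33 |

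The AUC0-last ratio is 11.33/32.38 = 35%. Both versions add Clast/λz = 4.31, so AUC0-∞ is 15.64 against 36.69, or 43%. %AUCex rises from 4.31/36.69 = 11.8% to 4.31/15.64 = 27.6%. The volume term is inflated by 36.69/15.64 = 2.35.

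Across half-lives:

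| Half-life (h) | AUC0-last, plus | AUC0-last, minus | Ratio | AUC0-∞ ratio | %AUCex, plus → minus | Volume factor |
|---|---|---|---|---|---|---|
| 2 | 3.19 | 1.04 | 33% | 33% | 0.0 → 0.0 | 3.07 |
| 8 | 13.70 | 6.25 | 46% | 46% | 0.2 → 0.4 | 2.19 |
| 12 | 19.69 | 8.82 | 45% | 46% | 1.3 → 3.0 | 2.20 |
| 24 | 32.38 | 11.33 | 35% | 43% | 11.8 → 27.6 | 2.35 |
| 48 | 45.71 | 9.83 | 22% | 49% | 34.8 → 71.3 | 2.05 |
| 96 | 56.45 | 6.55 | 12% | 64% | 59.3 → 92.6 | 1.56 |
| 168 | 62.39 | 4.19 | 7% | 76% | 74.3 → 97.7 | 1.32 |

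If 24 h were the last measurable sample, the AUC0-last ratio would be about 4% to 38% over half-lives of 4 to 72 h.

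**The case against.** **It may be a typing or reading error.** The defect is one character in a displayed equation, and the text was read from a PDF by a program. A rule that gives zero area to a flat profile would be recognised as a slip. This stands as a reason to check the source SAP first. It does not remove the conflict in the text as it reads.

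**The software would probably be right anyway.** Both AUC bullets cite the Phoenix WinNonLin manual, and a vendor using its built-in method would not need the printed equation. This also stands. A reader might infer that the reported AUC values are wrong, but neither document contains an AUC value, and nothing shows that the equation was programmed.

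**No single percentage belongs to this error.** A reader might quote one range for AUC as a whole, such as 12% to 53% of the true value. That range is AUC0-last against the analytic area for assumed half-lives of 96 down to 6 h. It does not describe AUC0-∞, where Clast/λz is added unchanged. The linear one-compartment model is also a simplification: Protocol 1.3 names target-mediated disposition as the main driver of clearance, and 1.3.2 reports non-linear elimination in monkeys. The objection to treating any such range as a finding stands.

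**The stakes are limited.** PK is not a listed Part 1 objective or endpoint. AUC is a listed endpoint only in Part 2, which will not be analysed. The trial stopped after no responses were seen, and the ADA–exposure plot in SAP 3.7.1 uses Cmax. All of this lowers the consequence, but the rule remains in force for the Part 1 PK parameters.

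**Linear or logarithmic trapezoids on the falling limb.** In the same model the correct-sign linear rule gives 119% of the true AUC0-last at a half-life of 6 h, 107% at 24 h and 100% at 96 h. A reader might treat this as part of the error. It is not: the linear rule is an accepted method. SAP 3.5.2 says no PK data were generated after 17 October 2023, and the SAP is dated 8 July 2024, so a change of method would come after the data.

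**Conclusion.** The point holds as a specification error. The equation that SAP 3.5.2 says is to be used is not the trapezoidal rule and contradicts the method cited in the same section. This needs no assumption about the drug. Applied literally, it would understate AUC0-last and AUC0-∞, inflate %AUCex wherever there is an extrapolated part, and overstate the volume term.

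The size is illustrative only. Under the stated model, over half-lives of 2 to 168 h, AUC0-last would be about 7% to 46% of the correct-sign trapezoid, AUC0-∞ about 33% to 76%, and the volume term about 1.3 to 3.1 times too large. These ranges rest on the assumed half-life, linear one-compartment kinetics, the infusion time carried over from the combination part, and a partly hidden sampling schedule. The documents do not establish that any result was miscalculated.

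**What to change.** 1. Check the sign in the source SAP.
2. If it is a minus, print AUC = (C1 + C2)/2 × (t2 − t1), or delete the equation and keep the software-manual reference.
3. Use the same description of the method in the AUC0-last and AUC0-∞ bullets, and have the PK vendor confirm that its software setting matches.
4. If the SAP is already in use, record the correction in the clinical study report.

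The cost is one line of SAP text and one confirmation from the vendor. No new data are needed, and no re-analysis unless the vendor did program the printed equation. Moving to linear-up/log-down is optional and should be recorded as a method choice if it is made.

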### 3.5.3 Serum Concentration

Raw serum concentration values will be summarized for the PK Population by study arm and dose level, visit and nominal time point using descriptive statistics, including the geometric mean and 68% range and grouped by cohort. For summaries of serum concentrations, below the limit of quantification (BLQ) values will be set to missing.

Individual and mean concentration versus time plots will be produced and displayed in linear and semi-logarithmic scales. The individual plots of all patients per cohort will be displayed in one graph. For the purposes of plotting the data, BLQ serum concentrations that are imbedded between two measurable concentrations or after the last measurable concentration will be set to

missing; however, BLQ values occurring prior to the first measurable concentration will be set to zero.

#### 3.5.4 Pharmacokinetics Parameters

Pharmacokinetic parameters will be analyzed based on the PK Population. For each patient, the PK parameters described in Section 3.5.1 will be determined by a non-compartmental approach. For the non-compartmental PK analysis, all serum concentration BLQ values occurring prior to the first measurable concentration will be set to zero. BLQ values occurring after the first measurable serum concentration will be set to missing.

PK parameters will be listed individually and summarized by study part and dose level using descriptive statistics including geometric mean and 68% range. Additional summaries of  $C_{max}$ ,  $AUC_s$ , and  $t_{1/2}$  might be done for subgroup analysis that may exclude patients having biased data specifically due to either the bioanalytical aspect or other issues identified and might be done in addition to the total data (totality of the data) and reported in the dedicated section of the study report.

### 3.6 Pharmacodynamic Assessments and exploratory Variables

Samples for Pharmacodynamic, biomarkers, and other exploratory samples will be drawn as indicated in the Schedule of Events in the protocol. Except indicated otherwise, Pharmacodynamic analysis will be performed based on the Pharmacodynamic population. Serum cytokines analysis will be performed based on the Safety Population.

The different biomarkers tested by Flow cytometry, as well as serum cytokines are represented in Appendix C. The list presented in the Appendix is an exhaustive list and may be changed depending on the availability of the data and the consent of patients.

The absolute counts per L blood of the immune cell populations determined by flow cytometry will be computed based on the % of each population per lymphocytes. If the parent population is not lymphocytes, the corresponding parent population will be used to calculate the % of each immune cell subpopulation per lymphocytes. The absolute count ( $10^6/L$ ) of each immune cell subpopulation will be calculated based on the determined percentage within lymphocytes and the lymphocytes count determined by Local labs. The different computation equations and populations are represented in Appendix D.

The change in the percentages or absolute values over time and fold change from baseline of selected biomarker will be summarized descriptively. Plots of the absolute values and the Fold change from Baseline will also be presented.

Individual pharmacodynamic and biomarkers data will be listed by patient.

### 3.7 Immunogenicity Assessment

Blood samples for anti-drug antibodies (ADA) will be drawn as indicated in the Schedule of Events in the protocol.

Number and percentage of prevalence and incidence of ADA, cross-reactivity with IL-2 (positive, negative), nAB will be presented as described in Section 3.1.4 based on the Immunogenicity Population at each visit. The number of patients at a visit with positive ADA and were previously negative will also be presented. The ADA titer for positive patients will be presented by a spaghetti plot in which timepoints that are nAB positive will be highlighted.

The impact of presence and titer of pre-existing, treatment-emergent, and treatment-boosted ADA and nAB on PK, safety, and efficacy read-outs will be evaluated by descriptive statistics.

A listing of all available immunogenicity data will be provided.

#### *3.7.1 Impact of ADA on $C_{max}$ , lymphocyte count and the pharmacodynamic response*

The median of all measured ADA titers across the study will be used to categorize ADA titer levels into ADA high and ADA low levels.

The impact of ADA levels on  $C_{max}$  will be analyzed based on the PK Population. The  $C_{max}$  of each patient will be plotted versus high and low ADA titer groups and will be grouped for Cycle 1 Day 1, Cycle 2 Day 1, and Cycle 3 Day 1.

The impact of ADA titer levels on the lymphocyte count will be analyzed by plotting the lymphocyte count grouped by ADA high versus low for Baseline, Cycle 1 Day 1, Cycle 1 Day 2, Cycle 1 Day 4, Cycle 1 Day 8, Cycle 2 Day 1, Cycle 2 Day 4, Cycle 3 Day 1, Cycle 4 Day 1, Cycle 5 Day 1, and Cycle 5 Day 4.

The impact of ADA on the pharmacodynamic response will be analyzed by plotting the percentage of Ki67+ NK cells and Ki67+ CD8 T cells of Cycle 2 Day 4 versus ADA titer level high and low and grouped by dose levels.

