8.2.5 Analysis of Immunogenicity

The impact of pre-existing, treatment-emergent, and treatment-boosted ADA on PK, safety, and efficacy read-outs will be evaluated by descriptive statistics and summarized in the Clinical Study Report.

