### Hematology

Absolute basophil value	Absolute eosinophil value
Absolute monocyte count	Absolute neutrophil count
Hematocrit	Hemoglobin
Lymphocyte count	Platelets
Red blood cell count	White blood cell count and differential [2]

2. Manual microscopic review is performed only if white blood cell count and/or differential values are out of reference range.

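### The Ki67 response at Cycle 2 Day 4 is plotted by high versus low ADA titre only, with no planned comparison against ADA-negative patients

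*SAP*

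**What the plan says.** SAP 3.7.1 creates two ADA levels with a single rule: "The median of all measured ADA titers across the study will be used to categorize ADA titer levels into ADA high and ADA low levels". It then uses those levels three times.

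- Cmax at Day 1 of Cycles 1, 2 and 3 "will be plotted versus high and low ADA titer groups".
- Lymphocytes are examined by "plotting the lymphocyte count grouped by ADA high versus low for Baseline" and a series of later visits up to Cycle 5 Day 4.
- The pharmacodynamic response is examined by "plotting the percentage of Ki67+ NK cells and Ki67+ CD8 T cells of Cycle 2 Day 4 versus ADA titer level high and low", further split by dose level.

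SAP 3.7 contains a broader commitment. It will describe "The impact of presence and titer of pre-existing, treatment-emergent, and treatment-boosted ADA and nAB on PK, safety, and efficacy read-outs". Protocol 8.2.5 names the same three targets: "The impact of pre-existing, treatment-emergent, and treatment-boosted ADA on PK, safety, and efficacy read-outs". Neither sentence lists pharmacodynamic read-outs. SAP 3.7 also indicates who has a titre to show: "The ADA titer for positive patients will be presented by a spaghetti plot".

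**The concern.** The last paragraph of SAP 3.7.1 sets out to show how ADA affect the pharmacodynamic response. The natural reference for that question is patients without ADA. A split by titre answers a narrower question: whether more antibody does more than less antibody. If ADA at any titre blunt Ki67 induction, both titre groups are blunted alike and the plot shows no difference.

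The matter is more than presentational. Protocol 6.11 rates an ADA response as moderately probable, so both positive and negative patients can be expected, and it tests whether the antibodies neutralise the drug in a cell assay. Ki67 on NK and CD8 T cells is where such neutralisation should show. SAP section 5 reports no responses in Part 1, so response rate by ADA status cannot show a difference, and pharmacodynamics carries more of the interpretation. The analyses that section 5 drops do not include those of 3.7.1.

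**Working it through.** The plan gives no figure to reproduce here. The check compares the texts and then illustrates the size with assumed ADA rates.

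**Step 1: which read-outs have a planned with/without-ADA comparison?**

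- Cmax: yes. It is a PK read-out, so the presence analysis in SAP 3.7 covers it.
- Lymphocyte count: possibly. "Lymphocyte count" is listed in the hematology panel of SAP Appendix B, so it can count as a safety read-out, although SAP 3.7 does not name it.
- Ki67+ NK and CD8 T cells: no. SAP 3.7 and Protocol 8.2.5 omit pharmacodynamics, SAP 3.6 summarises biomarkers without reference to ADA, and SAP 3.7.1 uses titre levels only.

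**Step 2: what do high and low mean?** The SAP does not say how negative samples are treated. There are two readings:

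- (a) Only positive samples carry a titre. Negative patients are then in neither group.
- (b) Negative samples count as zero. Low then contains them, and may consist of nothing else.

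**Step 3: illustration.** Inputs: N = 30, the Part 1 maximum (15 per arm, SAP 2.2.1.1). The ADA-positive share is assumed at 20% to 80%, with one titre per patient and an even split over two dose levels. For (b), the positive titres are assumed to be spread evenly over 10, 20, 40, 80, 160 and 320, and values equal to the median count as low.

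Formulas: positives = 30 × share; negatives = 30 − positives. In (a), each titre group = positives ÷ 2, and each titre-by-dose cell = positives ÷ 4. In (b), the negative fraction of low is p = negatives ÷ (all patients at or below the median).

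| Assumed share positive | Positive | Negative | (a) per titre group | (a) per titre group and dose | (b) median | (b) p |
|---|---|---|---|---|---|---|
| 20% | 6 | 24 | 3 | 1.5 | 0 | 24/24 = 1.00 |
| 40% | 12 | 18 | 6 | 3 | 0 | 18/18 = 1.00 |
| 60% | 18 | 12 | 9 | 4.5 | 15 | 12/15 = 0.80 |
| 80% | 24 | 6 | 12 | 6 | 40 | 6/18 = 0.33 |

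**Step 4: what would the plot show?** Suppose any ADA, whatever the titre, lowers the mean Ki67 percentage from μ to μ − δ.

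- Positive minus negative = −δ.
- Reading (a): high minus low = (μ − δ) − (μ − δ) = 0.
- Reading (b): high minus low = (μ − δ) − [pμ + (1 − p)(μ − δ)] = −pδ. That is the full δ at 20% or 40% positive, 0.80δ at 60% and 0.33δ at 80%.

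The same true effect can thus appear as anything from nothing to its full size, depending on a convention that the SAP leaves open.

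**Step 5: timing.** The notes to Protocol Table 20 place all ADA samples before dosing, apart from extra samples for an infusion-related or immune-related reaction, and require at least 12 days between treatments. Cycle 2 Day 4 therefore has no scheduled same-day titre. SAP 3.7.1 does not say which sample classifies that visit, or whether classification is per patient or per sample.

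**The case against.** A reader might infer that the SAP never compares patients with and without ADA. It does not support that: SAP 3.7 plans to describe the effect of ADA presence, and the titre plots in 3.7.1 add to that analysis without replacing it. Cmax is covered.

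A reader might also infer that lymphocytes have no reference at all. That goes too far. The count is a safety analyte, and its plot starts at Baseline, so a fall over cycles in both titre groups would be visible.

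Nor do the documents establish that negative patients are left out. Under reading (b) they are in the low group, and at low ADA rates they make up all of it. The group sizes in the table rest on assumed rates, and a median of titres divides patients into halves only if each contributes one titre.

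On consequences, these are descriptive plots with no formal testing (SAP 3.1.4). The trial stopped after Part 1, and SAP 3.5.2 says development in this indication will not be pursued. SAP 3.6 and 3.7 also provide biomarker and immunogenicity listings that could be matched by hand.

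All of this stands as a limit on the point. It leaves untouched that no section plans a with/without-ADA comparison for Ki67, and that the two titre labels have no fixed meaning.

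**Conclusion.** The point holds for the Ki67 response at Cycle 2 Day 4 and for the undefined handling of negative samples in the titre split. For Ki67, the stated method cannot reliably answer the question that SAP 3.7.1 poses. It does not hold as a claim that the SAP lacks any ADA-presence analysis, or that Cmax or lymphocyte count has no reference.

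The size cannot be fixed from the documents. Under the assumed rates and reading (a), 24 to 6 of 30 patients would be missing from the plot, and an effect common to all positive patients would show as zero. Under reading (b), the visible share of that effect would range from 100% to 33%, which also depends on the assumed titre spread. The point is minor: it concerns how a descriptive analysis is interpreted, and it affects no error rate, sample size or stated decision.

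**What to change.** In SAP 3.7.1:

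1. Plot three levels: ADA-negative, ADA-positive low titre and ADA-positive high titre.
2. Take the median over ADA-positive titres only.
3. Classify each plotted visit by the most recent ADA sample at or before it.

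The third rule lets a patient's group follow changing ADA status. A cut based on each patient's highest post-dose titre would be less suitable, because using it to assign groups would sort Baseline and early-cycle values by a later result.

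The cost is a few sentences of SAP text and one more level in plots already planned. No new samples are needed. The downside is small groups: with 20% of 30 patients positive, the Ki67 plot by dose level would average 1.5 patients per titre cell, so individual points should be shown and read with caution.
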